## 2. Purpose of the study

- a) **Provide a brief lay summary of the project in <200 words. The lay summary should be readily understandable to the general public.**

Surgery on the frontal sinus is done for patients who have sinus problems that do not respond to medications. It involves making an opening within the right and left frontal sinus of the nose to help it drain. For severe frontal sinus disease the sinus is widely opened and the left and right sinuses become one large sinus. This is done with sharp instruments and rigid endoscopes placed through the nostrils. While the sinus heals after surgery, a stent or steroids or both may be used to try to help make sure that the opening does not close back up. Two current options for this are Propel stents and steroid-soaked Nasopore. Propel stents are FDA-approved. Nasopore and kenalog injection are both FDA-approved, but their use together is part of the study and not specifically FDA-approved. A previous study shows that Propel stents are useful to reduce scarring in other frontal sinus procedures. We would like to know whether this is true in larger frontal sinus surgery where one common cavity is made and whether both steroid-containing stents are the same.

Page numbers from a sponsor's protocol/grant may be referenced in 2b and 2c.

- b) **List your research objectives (specific aims & hypotheses of the study).**

Aim 1: To compare the difference in mean post-operative SNOT-22 scores between the Propel stent and Nasopore groups.

Aim 2: To compare the incidence of other surgical postoperative complications (diagnosed post-operative CSF leak, epistaxis requiring treatment, adhesions) between Propel stent and Nasopore.

Aim 3: To ascertain the incidence of surgical complications based on the specific frontal sinus

**Protocol Title:** Randomized trial of Propel stent vs Kenalog-soaked Nasopore after Frontal Drill-out

---

pathology

Hypothesis: Patients in the Kenalog-soaked Nasopore group will have outcomes that are non-inferior compared to the Propel stent group when comparing the long term symptom control as measured by SNOT-22 scores at 24 months follow-up.

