**Please save frequently**

- c) **Describe the study design (e.g., single/double blind, parallel, crossover, control, experimental, observational, etc.). If the study is investigator-initiated, a timeline for individual subject recruitment, follow-up, and analysis for the study is required. Also, indicate if the subjects will be randomized.**

Single blind (Subject) randomized, active control study. Subjects will be randomized 1:1 using the rand function in Microsoft Excel program.

Timeline: There will be a 2 year recruitment period during which patients will be recruited and eligible to participate. Eligible patients are those with chronic inflammatory sinonasal disease for whom frontal drill out procedure is indicated after evaluation by otolaryngologist. Patients eligible for the study and consenting to participate will be randomly assigned to one of two treatment groups: 1) Nasopore group will receive frontal drill out procedure as indicated with Kenalog-soaked Nasopore stent applied to the post-operative outflow tract and 2) Propel stent group will receive frontal drill out procedure as indicated followed by Propel stent placement applied to the post-operative outflow tract.

After the surgery, we will ask patients to follow up 5 times: post-operatively once between week 1-2, once between week 6-8, month 6, month 12, and month 24. All visits are standard of care.

During those visits, patients will fill out a short research related questionnaire that will ask about whether or not their symptoms have improved after surgery. We will also assess sinus cavities with rigid nasal endoscopy. Surgical complications will be documented and SNOT-22 scores will be determined by patients filling out SNOT-22 questionnaire at each visit.

Preliminary analysis will be performed once 5 patients have been enrolled and then every 6 months thereafter until 2 years of follow up of the last subject. We expect enrollment to occur over a period of 2 years.

- d) **If subjects will be given placebo, please justify placebo use. \*?HELP?\***

N/A

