**Please save frequently**

Page numbers from a sponsor's protocol/grant may be referenced in 3b, 3c, and 3d.

- b) **Describe all the procedures, from screening through end-of-study, that the human subject must undergo in the research project, including study visits, drug treatments, randomization and the procedures that are part of standard of care. Specify which procedures are for research and which are standard of care. Please note: The box below is for text only. If you would like to add tables, charts, etc., attach those files in the Attachment section (#16).**

Patients who present with chronic inflammatory frontal sinus pathology with indication for frontal sinus surgery will be evaluated for frontal drill out candidacy per physician judgment and consented. Once consented, the patients will be randomized 1:1 using the "rand" function (random number generator) in Microsoft Excel program. Nasopore group will receive frontal drill out procedure as indicated with Kenalog-soaked Nasopore while the Propel stent group will receive the Propel Stent after frontal drillout. Lund-McKay CT staging system, a part of the standard of care, to determine overall and frontal sinus score will be used to help stage and evaluate patients pre-operatively. A preoperative SNOT-22 score, also done as standard of care, will be obtained to assess symptom burden. Those who undergo the procedure and have consented to participate in the study will be asked to present to the otolaryngology clinic for regularly scheduled follow-up as part of standard of care, where symptoms and complications will be assessed. Rigid nasal endoscopy and SNOT-22 score are standard of care for routine follow-up of patients with chronic inflammatory sinonasal disease and will be performed at each of the 5 visits: post-operatively 1-2 weeks, 6-8 weeks, month 6, month 12, and month 24. This data will be abstracted from the records for research purposes. The data collected from the medical record includes the patient's current ENT-related active medical problems.

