- d) **Describe how data analysis will be performed (statistical tests, methods of evaluating data) and indicate the smallest group/unit for which separate reporting will occur. For studies involving a questionnaire, if data and reliability information are available, please describe or provide references. For full board, unfunded studies describe sample size determination and power analysis. If none, please justify.**

The SNOT-22 score assesses symptomatic improvement and burden for patients with rhinosinusitis and is a clinically validated measure with high internal validity, correlation to its impact on quality of life, and longitudinal stability after sinus surgery. The minimal clinically important difference (MCID) for SNOT-22 is 9 points. [1, 2, 3, 4,5] From historical SLU otolaryngology practice data, patients who present to the otolaryngology clinic undergoing sinonasal surgery have a mean SNOT-22 score of  $42.0 \pm 8.0$ .

For this randomized, active control study of two types of sinonasal stents with steroid, we are interested in determining whether the cheaper and more available alternative (Nasopore and Kenalog) is similar to an accepted treatment (Propel stent) in symptom control at 24 months as measured by post-operative SNOT-22 scores.

For our sample size determination, we explore the lower limit of a 95% confidence interval (CI) around the mean difference between post-operative SNOT-22 scores of the two groups. We'll define the lower limit of the CI, or the margin of inferiority, as -8, which does not include the predetermined MCID of -9.  
We set power = 0.8 and alpha = 0.05.

Given: # subjects in each group =  $n = [(2(SD)^2) * (z_{1-(\alpha/2)} + z_{1-B})^2] / [(u_1 - u_2)^2]$  [ref 6]  
SD = 8.0, from SLU historical data  
 $[(z_{1-(\alpha/2)} + z_{1-B})]^2 = 7.8$ , estimated from z-tables,  $\alpha = 0.05$  and  $B = 0.2$

IF  $u_1 - u_2 = -8$  then  $n = 16$  subjects

To be conservative in our sample size calculation, we'll use  $u_1 - u_2 = -5$ , which yields a sample size of 40.

If we assume attrition rate of 10%, we estimate we'll need 45 subjects per group and a total of 90 subjects.

Difference in rates of complications will also be determined by chi-square testing for equality of proportions between groups. As these outcomes are expected to be few, our target sample size may not be adequate to determine statistical significance of differences. Reporting these complication rates nonetheless informs clinical practice.

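### Does the non-inferiority limit of -8 need a stated subtraction order and its own power figure?

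*Combined protocol and SAP*

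**What the plan says.** The hypothesis in section 2 (Purpose of the study), item b, is directional: "Patients in the Kenalog-soaked Nasopore group will have outcomes that are non-inferior compared to the Propel stent group", judged on SNOT-22 at 24 months. Aim 1 in the same item has no direction and happens to name Propel first: "To compare the difference in mean post-operative SNOT-22 scores between the Propel stent and Nasopore groups". The design text in item 2c lists the arms in the other order: "one of two treatment groups: 1) Nasopore group will receive frontal drill out procedure as indicated" and then "2) Propel stent group will receive frontal drill out procedure as indicated followed by Propel stent placement".

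The only decision limit is in section 3 (Study Procedures), item d: "We'll define the lower limit of the CI, or the margin of inferiority, as -8, which does not include the predetermined MCID of -9". The difference is written as u1 minus u2, and neither symbol is assigned to an arm. On the meaning of the score, item 3b says "A preoperative SNOT-22 score, also done as standard of care, will be obtained to assess symptom burden", and item 3d says "The SNOT-22 score assesses symptomatic improvement and burden for patients with rhinosinusitis". No sentence states outright that a higher score is worse.

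Item 3d sets power at 0.8 and alpha at 0.05 and takes an SD of 8.0 from practice data, in which "patients who present to the otolaryngology clinic undergoing sinonasal surgery have a mean SNOT-22 score of" 42.0 ± 8.0. It obtains 16 per group for a difference of -8. It then moves, calling the step conservative, to a difference of -5 for 40 per group, and adds 10% attrition for 45 per group and 90 in total.

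**The concern.** A one-limit rule means nothing until the difference has a sign. If the list numbering in item 2c is carried over to u1 and u2, or an analyst uses the habitual new-minus-control order, the difference is Nasopore minus Propel. A lower limit above -8 would then show that Propel is not much worse than Nasopore, which is the opposite of the hypothesis. Such a rule could pass a Nasopore arm that is clearly worse and fail one that is clearly better.

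The second worry is power. The protocol declares a margin of 8 but sizes the trial on 5, and it states no assumed true difference. A reader may wonder whether the 80% applies to the declared margin, or whether 5 was the margin intended.

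**Working it through.** **Inputs.** From item 3d: SD 8.0, alpha 0.05 two-sided (the formula uses z for 1 - alpha/2), power 0.8, margin 8, planning difference 5, attrition 10%. From item 2c: 1:1 allocation. SDs of 12 and 16 below are an assumed range, not protocol figures.

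**1. The protocol's own sample sizes.** n per group = 2 × SD² × 7.8 / difference².
- Difference 8: 2 × 64 × 7.8 / 64 = 15.6, so 16.
- Difference 5: 2 × 64 × 7.8 / 25 = 39.9, so 40. (With the unrounded 7.849 the result is 40.19, so 41, a negligible gap.)
- Attrition: 40 / 0.9 = 44.4, so 45 per group and 90 in total.

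All three agree with the text. The difference enters squared, so its sign has no effect on the sample size.

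**2. Which order the text implies.** Item 3d gives -8 the role of a limit on inferiority and writes the MCID as -9, so negative values stand for inferiority. Item 2b makes Nasopore the arm that might be inferior. Together these say that a negative difference means Nasopore is doing worse. If a higher score means more symptom burden, as items 3b and 3d indicate, that is Propel minus Nasopore. Under Nasopore minus Propel, -8 would mean Nasopore is 8 points better, which cannot be a limit on its inferiority.

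**3. What the order would do.** SE = 8 × √(2/40) = 1.789, and the half-width is 1.96 × 1.789 = 3.51. Let d be the true Nasopore disadvantage.
- Propel minus Nasopore: P(pass) = Φ((8 - d)/SE - 1.96).
- Nasopore minus Propel: P(pass) = Φ((8 + d)/SE - 1.96).

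| True state (SD 8, 40 per group) | Propel minus Nasopore | Reversed |
|---|---|---|
| Nasopore 8 points worse (d = 8) | 2.5% | above 99.99% |
| Equal arms (d = 0) | 99.4% | 99.4% |
| Nasopore 5 points better (d = -5) | above 99.99% | 38.9% |

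**4. What the 80% describes.** At 40 per group and SD 8:
- Difference of 5: Φ(5/1.789 - 1.96) = Φ(0.835) = 79.8%, which matches the stated 0.8.
- Margin 8, equal arms: Φ(8/1.789 - 1.96) = Φ(2.512) = 99.4%.
- Margin 8, Nasopore truly 3 points worse: 8 - 3 = 5, so again 79.8%.

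The t distribution gives 78.8% in place of 79.8% and 99.3% in place of 99.4%.

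**5. Sensitivity to the SD.** For margin 8 with equal arms, power is 84.6% at SD 12 (SE 2.683) and 60.9% at SD 16 (SE 3.578). It stays at 80% up to SD = 8 / (2.802 × √(2/40)) = 12.8.

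**The case for a change.** The best case for a change is that the protocol's only numbering of the arms points the wrong way, that new minus control is a common default, and that the two orders give opposite tests. Item 3c also plans analyses from the fifth patient onwards, with stopping for inferiority or superiority, so the sign ought to be settled before data are seen. On power, calling 5 conservative explains why the sample is larger but not which scenario the trial is powered for. The SD comes from patients presenting for surgery and not from 24-month scores.

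Part of this stands. The subtraction order is nowhere defined, and the direction of the score has to be inferred from the word burden. But the numbers in item 2c only enumerate a list and are never tied to u1 and u2. An analyst who prefers Nasopore minus Propel would, to test the stated hypothesis, check the upper limit against +8, which is the same test. The reversed figures in the table describe a rule that conflicts with item 2b.

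On power, the move from 8 to 5 is made openly and only -8 is called a margin. If 5 had been meant as the margin, the conclusion would change for an observed Nasopore disadvantage between 5 - 3.51 = 1.49 and 8 - 3.51 = 4.49 points, but nothing in the text supports that reading. Whether SD 8 suits 24-month scores is a fair question, but a separate one. It is also a reason not to put 99% into the protocol as a firm figure.

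**Conclusion.** No change follows. The sign is a missing definition that the protocol's own hypothesis and its use of negative values for inferiority fill in only one way: Propel minus Nasopore, with non-inferiority claimed if the lower 95% limit lies above -8. Read so, the rule passes a Nasopore arm that is truly 8 points worse 2.5% of the time, as intended. This rests on a higher SNOT-22 score meaning more burden, which the text indicates but does not state.

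The power statement contains no error. It is right (79.8%) for the 5-point difference it was computed from, and the protocol never claims 80% at the margin of 8. At that margin power is 99.4%, given SD 8, 40 evaluable per group, equal arms and one fixed-sample analysis that ignores the planned interim looks. Printing that figure would alter neither the sample size nor any result. A clause naming the order of subtraction would be a courtesy to readers, and the analysis does not depend on it.

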**Please save frequently**

- e) **State if deception (including incomplete disclosure of study purpose/procedures) will be used. If so, describe the nature of the deception and provide a rationale for its use. Also, describe debriefing procedures or justify a waiver of the requirement to debrief. NOTE: for studies using deception, an alteration of consent must be justified in the Informed Consent section of the protocol (#13) and the debriefing script/statement must be uploaded in the Attachments section (#16). See IRB Deception Guidelines.**
- f) **Is there an accepted standard of care and/or standard practice at SLU for the condition/disease/situation being studied? This information will assist in comparing the risk/benefit ratio of study procedures relevant to usual care that would be received outside of the research context. \*?HELP?\*** Y

**If yes, please describe the standard of care and standard practice at SLU for the condition/disease/situation being studied.**

Pre-operative CT scan is standard of care for patients with chronic inflammatory frontal sinus pathology who are going to undergo surgery.  
There is no specific standard of care for follow-up of chronic inflammatory sinonasal pathology and is left up to the discretion of the attending otolaryngologist. The standard of care for follow-up of chronic inflammatory sinonasal disease in SLU rhinology practice is what is proposed in this study (post-op week 1-2, week 6-8, month 6, month 12, month 24, and yearly thereafter). SNOT-22 questionnaire is standard of care for every patient at every visit in SLU rhinology practice.  
The standard of care for use of Propel stent and nasopore placement as well as topical nasal steroid at the discretion of the attending surgeon and based on patient's disease process, and these or a combination of these are routinely used in a large number of patients in a variety of procedures currently.  
Rigid nasal endoscopy is standard of care at all follow-up visits for all patients with chronic inflammatory sinonasal disease.  
As standard of care, patients may receive post-operative oral steroids or antibiotics based on intra-operative findings or the discretion of the attending surgeon. Strong evidence for or against use of antibiotics or oral steroids after sinus surgery is not found in the literature and it is considered an option based on current guidelines.[1]  
The only non-standard of care portion of the protocol is placement of Kenalog within Nasopore.


- g) **Does this study involve any diagnostic imaging, labwork or genetic testing that could result in clinical discovery (diagnoses, genetic mutations, etc.)? Note that this could include discovery that is expected (related to the research) or incidental (not related to research aims, but possible, like a mass/shadow found in imaging despite not looking for it).** Y

**Protocol Title:** Randomized trial of Propel stent vs Kenalog-soaked Nasopore after Frontal Drill-out

---

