Note that to maintain uniformity in care, post-operative antibiotics (defined as up to day 60 post-op) will only be given to patients in any group if frank purulence is noted intra-operatively. In addition, in accordance with other trials involving drug eluting stents [1], oral and topic steroids will not be given to patients in any group until 60 days post-operatively. Because oral steroids and certain antibiotics have anti-inflammatory properties, this could confound the result of the study. For this reason, we wish to avoid using them in a random fashion.

- c) **If the proposed study is a clinical trial where a drug, vaccine, device or other treatment is compared to a placebo group or comparison treatment group, what are the guidelines or endpoints by which early decisions regarding efficacy or lack of efficacy can be made? For example, it may be reasonable to stop enrollment on a study when efficacy has already been clearly demonstrated, to avoid unnecessary enrollments of additional subjects. Alternatively, it may be reasonable to stop enrollment when it is clear that efficacy will never be demonstrated, given the statistical power of the study as designed. Describe the guidelines that are in place to assist in making these determinations, if relevant to the proposed study.**

A difference in mean post-operative SNOT-22 score of 9 points will be considered a clinically significant difference. [1]

As such, preliminary analyses will be performed once 5 patients have been enrolled and then every 6 months thereafter until 2 years of follow up of the last subject. If clear statistically significant inferiority or superiority is demonstrated, the trial will be stopped.

[1] Chowdhury NI, Mace JC, Bodner TE, et al. Investigating the minimal clinically important

**Protocol Title:** Randomized trial of Propel stent vs Kenalog-soaked Nasopore after Frontal Drill-out

difference for SNOT-22 symptom domains in surgically managed chronic rhinosinusitis. Int Forum Allergy Rhinol. 2017;7(12):1149-1155.

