**Protocol Title:** Randomized trial of Propel stent vs Kenalog-soaked Nasopore after Frontal Drill-out

---

investigational, and non-invasive procedures (e.g., surgery, blood draws, treadmill tests).

There are no aspects of this study that involve risk of harm or discomfort greater than ordinarily encountered in the standard course of the participants' medical treatment in patients for whom frontal drill out is indicated regardless of study participation. Frontal drillout complications may include epistaxis, orbital/periorbital ecchymoses and emphysema, dental pain, adhesions, hyposmia, and stenosis, meningitis and brain abscess and intraoperative trauma. Intraoperative trauma may cause CSF leaks, intraorbital hemorrhage, diplopia, blindness, epiphora, intracranial injury, stroke, tension pneumocephalus, significant epistaxis, and anosmia. There is always the risk of developing previously unknown side effects. Patients may encounter these risks regardless of participation in this research study. The investigator is willing to discuss any questions the participant may have about these risks and discomforts.

6. Describe any risks related to the use of radioisotopes/radiation-producing machines (e.g., X-rays, CT scans, fluoroscopy).

7. Describe why this investigational compound/drug/device/procedure's risks/benefits are potentially better than standard of care or other common alternatives. Any standard treatment that is being withheld must be disclosed and the information must be included in the consent form. **\*?HELP?\***

No standard treatment is being withheld. We are attempting to determine which device used in the standard of care is more beneficial than the alternative.

8. Describe any psychological, social, or legal risks the subject may experience. **\*?HELP?\***

Breach of Confidentiality

Information will be kept under lock and key with password protection on the computer. Coding will be used with no patient identifiers attached to confidential information. Even with these precautions, breach of confidentiality is a risk.

Use of Questionnaires:

Some questions in the questionnaires may make subjects feel uncomfortable. Subjects may choose not to answer any question with which he/she feels uncomfortable.

Page numbers from a sponsor's protocol/grant may be referenced in 9.9 and 9.10.

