**\*\*\* Benefits/Alternatives, Procedures to Maintain Confidentiality and Privacy \*\*\***

**10. Benefits/Alternatives**

a) **Benefits.** Describe the potential benefit(s) to be gained by the subjects and how the results of the study may benefit future subjects and/or society in general. Indicate if there is no direct benefit to the participants.

a.) Subjects will not benefit from the research.  
b.) Society may benefit from research findings because they will provide physicians with evidence of the effectiveness of the two devices and help them make well educated decisions about which device is best in practice

b) **Alternatives.** Describe any alternative treatments and procedures available to the subjects should they choose not to participate in the study. If no such alternatives exist, please state that the alternative is nonparticipation. For some studies, such as record reviews, a description of alternatives would not be applicable.

The alternative is non-participation in the study. The patient will still undergo your sinus surgery as planned and receive one of the two stents described in this study, Propel or Nasopore, as determined by [name].

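### Section 3b removes the surgeon's discretion over steroids and antibiotics to day 60, but 3f and 9.7 tell the IRB that nothing else is non-standard and nothing is withheld

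*Combined protocol and SAP*

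**What the plan says.** Section 3b (Study Procedures) sets two co-medication rules for both arms. On steroids: "oral and topic steroids will not be given to patients in any group until 60 days post-operatively". On antibiotics, the post-operative rule is: "antibiotics (defined as up to day 60 post-op) will only be given to patients in any group if frank purulence is noted intra-operatively". The reason given is a research one: "Because oral steroids and certain antibiotics have anti-inflammatory properties, this could confound the result of the study".

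Section 3f describes usual care at the site: "As standard of care, patients may receive post-operative oral steroids or antibiotics based on intra-operative findings or the discretion of the attending surgeon". It also leaves topical nasal steroid to the attending surgeon, and it notes that strong evidence on oral steroids and antibiotics is lacking in either direction. It then ends: "The only non-standard of care portion of the protocol is placement of Kenalog within Nasopore".

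The prompt for section 9.7 (Risks, item 7) says: "Any standard treatment that is being withheld must be disclosed and the information must be included in the consent form". The answer begins: "No standard treatment is being withheld".

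Section 9.9 (Special Precautions) says that complications will receive the medical care they need, on the clinician's judgment. Section 3b does not refer to it.

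**The concern.** The 3f and 9.7 answers are where the IRB compares trial care with usual care. The 3f prompt says that its answer serves that comparison, and 9.7 is the specific question about withheld treatment. If both answers omit a restriction that 3b imposes for research purposes, the comparison is incomplete at the places designed to make it.

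There is a second, smaller issue for the treating clinician. The only antibiotic exception in 3b is a finding made during surgery. Taken literally, it does not cover an infection that first appears at, say, week 3. Section 9.9 says necessary treatment will be given. The two sections should agree on the page, so that nobody has to choose between treating a patient and following 3b.

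**Working it through.** No figure in the plan is at issue, so the check is a comparison of the texts plus one reading of the calendar.

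**Step 1: is the restricted care part of usual care?**

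| Treatment | Usual care (3f) | In the trial to day 60 (3b) |
|---|---|---|
| Oral steroids | Allowed, on findings at surgery or surgeon's discretion | Not given |
| Topical steroids | Allowed, surgeon's discretion | Not given |
| Antibiotics, frank purulence at surgery | Allowed | Allowed |
| Antibiotics, no frank purulence at surgery | Allowed, on other findings at surgery or surgeon's discretion | Not given |

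Three of the four rows differ. In each, a choice that 3f places under standard of care becomes a fixed rule. The third row does not differ, because a rule based on purulence seen at surgery is itself one of the routes that 3f describes. The non-standard element is therefore the loss of discretion, not the whole antibiotic rule.

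**Step 2: do the disclosure answers reflect this?** The last sentence of 3f says that there is only one non-standard element and names Kenalog in Nasopore. Step 1 shows another. The 9.7 answer says that nothing standard is withheld; step 1 shows three discretionary options that are.

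**Step 3: how far does the restriction reach?** It covers both arms, so all 90 planned patients. The visits are at weeks 1-2, weeks 6-8 and months 6, 12 and 24. In days, weeks 1-2 are 1 × 7 = 7 to 2 × 7 = 14, and weeks 6-8 are 6 × 7 = 42 to 8 × 7 = 56. Both fall before day 60 and the other three fall after it, so the restriction spans 2 of the 5 visits.

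**Step 4: does 3b allow rescue treatment?** Section 3b defines post-operative antibiotics by time (to day 60), not by purpose, and permits them only on the finding at surgery. It states no exception for later infection, and none for steroids. Section 9.9 promises necessary treatment without naming drugs. Section 3b opens its rule with a wish for uniform care and closes it by saying that haphazard use is what it wants to avoid. Together these suggest that rescue treatment was meant to be allowed. The gap is that 3b does not say so.

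**The case against.** The best reply is that optional care is not withheld care. Section 3f says that patients may receive these drugs, that strong evidence is lacking, and that guidelines treat them as an option. Not giving an option is also within standard practice, and the rest of the 9.7 answer is about the devices, so its author was probably thinking of the stents. Section 3b also states the restriction and its reason openly in the same application.

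Much of this stands, and it keeps the point minor. It does not make the two answers accurate. Section 3f itself uses the standard-of-care label, usual care is a decision for each patient, and 3b replaces that decision with a rule adopted for the study. Stating the rule in 3b does not correct the answers that say otherwise.

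A reader might infer more than the documents support:

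- *That the trial forbids treating a post-operative infection.* The literal wording of 3b permits that reading, but 9.9 and the stated aim of 3b point the other way. It is an ambiguity to clear up, not a ban.
- *That section 10b is also wrong.* It says that patients outside the trial will "receive one of the two stents described in this study, Propel or Nasopore". It does not mention discretionary drugs, but nothing in it is false, and no change there is needed.
- *That the adverse event rates in 9.4 size the problem.* They carry no time window and use different terms for the two products, so they do not show how many infections would fall before day 60.

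**Conclusion.** The inconsistency is real and minor. Section 3b removes the surgeon's usual discretion over oral and topical steroids, and over antibiotics without frank purulence at surgery, to day 60 in both arms. The last sentence of 3f and the 9.7 answer do not reflect this. The restriction reaches all 90 planned patients and 2 of 5 visits. The missing rescue exception in 3b is a clarification, since 9.9 probably already intends it.

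The conclusion rests on 3f's own description of usual care at the site and on reading the steroid rule as applying to steroids other than the one in the study product.

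The restriction itself may well be sound: it applies equally to both arms and has a stated reason. A reader might infer that it biases the 24-month SNOT-22 comparison; nothing in the documents shows that, and no such effect is claimed. Nor can it be said that patients are not told. The consent form is not among the documents available here, so whether it names the restriction is unknown.

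**What to change.** 1. **Section 3f, last sentence.** Replace with: *The non-standard portions are Kenalog within Nasopore and, to day 60, removal of the surgeon's discretion to give oral or topical steroids, or antibiotics without frank purulence at surgery.*
2. **Section 9.7.** State that these discretionary treatments are withheld to day 60 in both arms.
3. **Consent form.** Check that it names the 60-day restriction, as the 9.7 prompt requires; add it if it does not.
4. **Section 3b.** Add: *Antibiotics for a diagnosed post-operative infection, and steroids only where medically necessary for a serious adverse event, are allowed; record drug, date, reason and arm.*

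The exception should stay this narrow. Section 9.4 lists events such as nasal congestion, asthma and nasal polyps, for which a clinician might use a steroid. A clause covering any adverse event could bring back the early steroid use that 3b sets out to exclude.

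The cost is one sentence in each of three sections, the consent check, and a few extra items to record. Sample size and analysis do not change. The co-medication rule is loosened slightly, so a few patients may have an early anti-inflammatory exposure. Recording each use by arm lets the investigators see how many there were and whether the arms differ.
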